Title: attending physician

Address: [name]
Shanghai postal code: 200040

[contact]

mobile [contact]

email [contact]

一、 Programme summary

Protocol name	The efficacy and safety of metformin intervention in elderly overweight or obesity with mild cognitive impairment
Version number/ Version date	V1.0 7 August, 2025
Research objects	Elderly overweight or obesity patients with mild cognitive impairment
Research purposes	To explore the efficacy and safety of metformin in sufficient amount in elderly overweight or obese patients with MCI. To provide reliable evidence for the elderly overweight or obese patients with MCI to delay and reverse the cognitive dysfunction.
Research design	This study was a prospective, randomized controlled, single-center clinical cohort study. Elderly subjects who were overweight or obese with MCI and met the inclusion criteria and did not meet the exclusion criteria were included in this study with informed consent. The subjects were randomly divided into two groups using random number method. In the first group, subjects received metformin sustained-release tablets (1500mg once a day or reduced to the maximum tolerated dose if intolerable) and lifestyle intervention guidance. Subjects in the second group received only lifestyle intervention guidance. All subjects were followed for a period of 26 weeks. History collection, body measurement index evaluation, glycolipid metabolism biochemical test, medication record, and MoCA scale evaluation were conducted during the enrollment phase and the end of follow-up. The insulin sensitivity in central nervous system of subjects in the two groups before and after treatment was evaluated by nasal insulin inhalation combined with fMRI.
Inclusion/ exclusion	Inclusion criteria

criteria	
A. age: 60 -75 years;
 
B. Body mass index: $\geq 24 \text{kg/m}^2$;
 
C. glycated hemoglobin $< 8.5\%$;
 
D. The scores of the MoCA scale are 20–26 (education > 10 years) or 20–25 (education ≤ 10 years);
 
E. sign informed consent forms;
 
Exclusion criteria
 
A. Anyone who takes any hypoglycemic drug within 8 weeks prior to enrollment;
 
B. type 1 diabetes;
 
C. Central nervous system magnetic resonance imaging cannot be completed;
 
D. A history of alcohol or drug addiction;
 
E. Severe gastrointestinal diseases, history of gastrointestinal surgery, severe cardiopulmonary dysfunction, malignant tumor and other diseases;
 
F. Abnormal liver function (liver enzyme index is more than 2.5 times the upper limit of the reference range) or renal function (estimated glomerular filtration rate $< 45 \text{ mL/min}$);
 
G. There were relevant situations that the investigator judged were not suitable for inclusion in the study.

Study drug	
Drug name: metformin hydrochloride sustained-release tablets (Gehuazhi)
 
Drug specification: 500mg

Sample size	
The change in blood flow volume of cerebral regions shown by fMRI after nasal insulin inhalation was used as the research endpoint. According to the results of previous literature, the difference between groups after drug intervention was 20%, and the standard deviation was 20%. When the accuracy was 0.05 and the test efficiency $1-\beta$ was 0.8, the required sample size for each group was obtained from the sample size calculation formula: $n_1=n_2=23$. Considering the existence of a certain shedding ratio, and calculated based on the shedding rate of 15%, 54 patients, 27 in each group, were to be included in the study.

Statistical method	
SPSS 22.0 statistical analysis software was used for calculation. All statistical tests were performed using a two-sided test, and $P \leq 0.05$ was considered statistically significant for the difference tested. Enumeration data were described by constituent ratio, and measurement data were described by mean, standard deviation, median, and interquartile. Statistical analysis: Appropriate methods were used for analysis according to the types of indicators. T test or Wilcoxon rank sum test was used for inter-group comparison of quantitative data, and chi-square test was used for classified data.

---------------------------	--

二、Contents

二、	Programme summary	4

Cognitive impairment refers to one or more impairments in learning and memory, language, executive function, sensorimotor function, complex attention and social cognition, which is often accompanied by mental, behavioral and personality abnormalities, including mild cognitive impairment (MCI) and dementia [1]. Epidemiological studies have shown that the prevalence of MCI in people over 60 years old in China is 15.5%, and the number of people with MCI is 38 million [2]. More studies have confirmed the existence of a clear correlation between obesity and cognitive impairment [3]. Patients with MCI have less interference with cognitive deficits in daily life, but the proportion of patients progressing to dementia every year can reach 5-10%, which is much higher than the incidence rate of 1-2% of the general population every year [4]. 50% of patients with MCI can develop to dementia within five years [5], and 20-30% of patients with MCI can recover to normal cognition [6].

Therefore, early detection of MCI and timely intervention for elderly obese patients have important clinical significance and value.

2. Central nervous insulin resistance plays a role in the pathogenesis of cognitive dysfunction. Functional magnetic resonance imaging (fMRI) can evaluate cognitive dysfunction by observing central insulin resistance.

At present, the mechanisms of cognitive dysfunction in elderly obese patients include the pathophysiological role of microvascular mechanisms and fat-derived factors [3]. Insulin not only regulates peripheral metabolism, but also acts on the central nervous system to regulate cognitive function. All cell types in the brain have insulin signaling pathways, and some studies have shown that insulin resistance in the brain can damage the plasticity and memory function of hippocampal synapses, leading to cognitive decline [7]. The Montreal Cognitive Assessment Scale (MoCA) is usually used for the evaluation of cognitive function, which includes multiple dimensions such as memory, attention, executive function and language function, with a full score of 30. The score considering the diagnosis of MCI is 20-26 (education > 10 years) or 20-25 (education \leq 10 years) [8]. However, in actual work, scale collection is affected by many factors. fMRI can display the changes of local cerebral blood flow and metabolic activities before the changes of brain structure, so as to understand the changes of brain function in depth. It is an important means for early diagnosis of cognitive dysfunction, efficacy monitoring and mechanism research [9]. The degree of central insulin resistance was assessed by fMRI combined with nasal insulin inhalation to observe the response of different brain regions to insulin. The absence of neuroimaging or neurophysiological reactions after nasal insulin inhalation is suggestive of central nervous system insulin resistance [7]. Previous studies have shown that improving central insulin resistance can delay or even reverse cognitive decline [10]. Therefore, the central insulin resistance observed by fMRI can be used as an objective basis for the assessment of cognitive function.

3. Metformin may improve cognitive dysfunction by improving central insulin resistance in elderly obese patients.

Metformin is widely used as the first-line medication for type 2 diabetes. Basic research showed that metformin had the potential to activate the 5'AMP-activated protein kinase (AMPK) pathway, which played a vital role in the pathogenesis of dementia [11]. Metformin can improve insulin resistance [12], reduce neuronal apoptosis [13], and reduce cerebral oxidative stress and inflammatory response [14]. Recent studies have shown that the use of metformin is associated with a significant

reduction in the risk of dementia in elderly patients with type 2 diabetes [15][16], but these studies are all diabetes patients in a large database. Comparing the use of metformin to reach the conclusion is subject to more interference factors. Other early studies have shown that long-term use of metformin even increases the risk of dementia [17], which may be related to vitamin B12 deficiency, the duration of metformin use, and the course of diabetes. Short-term controlled studies with small samples have shown that metformin can penetrate the blood-brain barrier and improve learning, memory and attention in non-diabetic MCI patients [18].

In summary, as a widely used traditional hypoglycemic drug, metformin has been shown to improve central insulin resistance in basic studies and has been proved to be feasible in clinical studies of diabetic patients. However, there are few studies investigating the efficacy of metformin in improving cognitive function in elderly obese patients with MCI.

七、 Research method

1. overall design

This study was a prospective, randomized controlled, single-center clinical cohort study. Those subjects who met the inclusion criteria were included in the study after they signed the informed consent. The study was conducted in the Drug Clinical Laboratory of Endocrinology Department, Huadong Hospital. The subjects were randomly divided into two groups using random number method. In the first group, subjects received metformin sustained-release tablets (1500mg once a day or reduced to the maximum tolerated dose if intolerable) and lifestyle intervention guidance. Subjects in the second group received only lifestyle intervention guidance. All subjects were followed up for 26 weeks with a diary card for dosing and adverse events and a telephone visit every 4 weeks 3 days after randomization.

2. Study Population

Any elderly subject who is overweight or obesity with mild cognitive impairment and is admitted to the study center may be considered for this study. The primary investigator bore the primary responsibility for subject enrollment. You can expect to limit the speed of grouping for the following reasons:

- The number of outpatient visits and the number of subjects who met the inclusion and exclusion criteria;
- The willingness and informed consent of the subjects were evaluated at baseline.

八、 Inclusion criteria, exclusion criteria and exit criteria of subjects

1. Inclusion criteria

- A. age: 60 -75 years;
- B. Body mass index: $\geq 24\text{kg}/\text{m}^2$;
- C. glycated hemoglobin $< 8.5\%$;
- D. The scores of the MoCA scale are 20–26 (education > 10 years) or 20–25 (education ≤ 10 years);
- E. sign informed consent forms;

2. Exclusion criteria

- A. Anyone who takes any hypoglycemic drug within 8 weeks prior to enrollment;
- B. type 1 diabetes;
- C. Central nervous system magnetic resonance imaging cannot be completed;
- D. A history of alcohol or drug addiction;
- E. Severe gastrointestinal diseases, history of gastrointestinal surgery, severe cardiopulmonary dysfunction, malignant tumor and other diseases;
- F. Abnormal liver function (liver enzyme index is more than 2.5 times the upper limit of the reference range) or renal function (estimated glomerular filtration rate $< 45\text{ mL/min}$);
- G. There were relevant situations that the investigator judged were not suitable for inclusion in the study.

3. Exit criteria

All subjects had the right to withdraw from the study at any stage of the study and the investigator had the right to discontinue observation of subjects who:

- 1) Continuing to participate in the seminar would cause unnecessary damages to the subjects;
- 2) The subjects had poor compliance and did not cooperate with the researchers in

relevant examinations and interventions;

- 3) Subjects who were found not to meet the inclusion criteria after participating in the study;
- 4) Subjects who were found to meet the exclusion criteria after participation in the study.

九、 Sample size assessment

The change in blood flow volume of cerebral regions shown by fMRI after nasal insulin inhalation was used as the research endpoint. According to the results of previous literature, the difference between groups after drug intervention was 20%, and the standard deviation was 20%. When the accuracy was 0.05 and the test efficiency $1-\beta$ was 0.8, the required sample size for each group was obtained from the sample size calculation formula: $n_1=n_2=23$. Considering the existence of a certain shedding ratio, and calculated based on the shedding rate of 15%, 54 patients, 27 in each group, were to be included in the study.

十、 Study Endpoints

1. Effectiveness

The main evaluation indexes were the changes of cerebral blood flow shown by fMRI after nasal insulin inhalation. The secondary evaluation index was MoCA scale score. To explore the influence of metformin intervention on cognitive dysfunction under different glycosylated hemoglobin baselines.

2. Safety

Intestinal reaction, such as abdominal pain, diarrhea, abdominal distension; other uncomfortable symptoms or events affecting living activities.

十一、 Research process

1. **Screening period:** whether the screening met the inclusion criteria, and there was no exclusion criterion.
2. **V0:** A total of 54 elderly subjects who were expected to be enrolled as overweight or obesity with MCI, taking medical history (previous illness, medication history and concomitant medication, smoking history, alcohol consumption history, and educational level), demographic data (gender, date of birth), comprehensive physical examination (height, weight, body temperature, heart rate, respiration, blood pressure, waist circumference, hip circumference, body composition, nervous system, and cardiopulmonary abdomen), Laboratory tests (fasting blood glucose, fasting insulin, fasting C-peptide, glycated hemoglobin, blood lipids, routine blood tests, liver and kidney function, and routine 12-lead electrocardiogram), MoCA scale evaluation, and nasal insulin inhalation combined with fMRI imaging were performed.
54 patients were randomly divided into two groups. In the first group, subjects received metformin sustained-release tablets (1500mg once a day or reduced to the maximum tolerated dose if intolerable) and lifestyle intervention. Subjects in the second group received only lifestyle intervention guidance. All subjects were followed for a 26-week follow-up period and diary cards were issued to record dosing and adverse events. A 24-hour meal was recorded during the first week of intervention; Exercise instruction.
3. **V1** (intervention 4 weeks): The patient was interviewed by phone for any adverse events.
4. **V2** (eight weeks of intervention): The patient was interviewed by phone for any adverse events.
5. **V3** (intervention 12 weeks): The patient was interviewed by phone for any adverse events.
6. **V4** (intervention for 16 weeks): The patient was interviewed by phone for any adverse events.

7. **V5** (intervention of 20 weeks): The patient was interviewed by phone for any adverse events.

8. **V6** (24 weeks of intervention): The patient was interviewed by phone for any adverse events.

9. **V7** (intervention for 26 weeks): Medical history (previous disease history, medication history and concomitant medication history, smoking history, drinking history, and educational level) demographic data (gender, date of birth), comprehensive physical examination (height, weight, temperature, heart rate, respiration, blood pressure, waist circumference, hip circumference, body composition, nervous system, and cardiopulmonary abdomen), laboratory tests (fasting blood glucose, fasting insulin, fasting C-peptide, glycated hemoglobin, blood lipid, blood routine, liver and kidney function, routine 12-lead electrocardiogram), MoCA scale evaluation, and nasal insulin inhalation combined with fMRI imaging were collected again.

10. **V8**: A safety visit 4 weeks after the end of the intervention to ask the patient over the phone for any adverse events. The report was analyzed and recommendations were made for treatment protocol adjustments based on the report.

[figure not shown]

Figure 1 research flow chart

visit	V-1	VO	V1	V2	V3	V4	V5	V6	V7	V8
stage	screening period	baseline visit	telephone follow-up	follow-up at the end of the treatment period	follow-up after the treatment period					
time(weeks)	2	0	4	8	12	16	20	24	26	30
window period (days)			±3d	±3d	±3d	±3d	±3d	±3d		±7d
sign the informed consent form	√									
check the inclusion and exclusion criteria	√	√								
formulate or adjust the medication plan for lowering blood glucose		√								
collect medical history (previous illness, medication history and concomitant medication, smoking history, alcohol consumption history, and educational level)			√						√	
demographic data (gender, date of birth)			√						√	
comprehensive physical examination (height, weight, body temperature, heart rate, respiration, blood pressure, waist circumference, hip circumference, nervous system, and cardiopulmonary abdomen)			√						√	
body composition			√						√	
routine 12-lead electrocardiogram		√							√	
routine blood tests		√							√	
liver and kidney function, eGFR(based on renal function assessment)			√						√	
blood lipids(CHO, TG, HDL-C, and LDL-C)			√						√	
fasting blood glucose, fasting insulin, fasting C-peptide			√						√	
HbA1c			√						√	
MoCA scale evaluation			√						√	
nasal insulin inhalation combined with fMRI imaging			√						√	
diet and exercise guidance		√								
record adverse events		√	√	√	√	√	√	√	√	

Figure 2 Follow-up plan (duration and content of follow-up)

Note:

- (1) After a 5-minute rest, systolic and diastolic blood pressure as well as pulse were measured by sitting quietly. Blood pressure, waist circumference, grip strength, and body function were assessed using the uniform method provided. The body composition was determined using Beijing Yueqi BIA-140.
- (2) All tests were performed in the test center. There were two blood tests in total, and 5ml venous whole blood was drawn each time.
- (3) ECG: 12 leads were used, and the same subject should be kept consistent.
- (4) Early withdrawal from trial visit: Participants who withdrew from the trial early should return to the study center on an empty stomach for the early withdrawal visit within 7 days after the investigator was informed. A repeat examination for the same item may be waived if the visit is less than 7 days from the date of the previous visit.
- (5) Dietary life guidance rules: during the formulation of nutrition treatment plan, attention should be paid to appropriately increase the protein and energy intake, to encourage the elderly subjects to choose regular exercise that can be insisted on for a long time, and to select the appropriate exercise mode (such as aerobic exercise and resistance training).

十二、 Serious adverse events

Definition of adverse event (AE): Any adverse medical event that occurred between the time the subject signed the informed consent and was enrolled in the study and the last visit, regardless of causality to study drug, was considered an adverse event. Serious adverse events (SAE) was a clinical event indicating a significant hazard, contraindication, side effect, or caution with respect to a test article

at any dose or at any time during observation. Adverse events are classified as serious adverse events if one or more of the following criteria are met: 1. Death 2. Life-threatening (meaning that the patient in whom the event occurred was at risk of dying immediately at the time of the event; Does not include those events which, if more serious, could result in the death of the patient) 3. Lead to hospitalization or prolonged hospitalization 4. Lead to permanent or significant loss of labor or disability 5. Congenital malformations. Medical events that have not yet resulted in death, life risk, or hospitalization that, after appropriate medical judgment, may be hazardous to the patient or subject or require medical or surgical treatment to avoid such occurrences should also be considered SAE.

If any adverse event occurs, the patient should report it to the researcher in time. The researcher should make a detailed record at the corresponding position on the case report form. The researcher should assist the patient to actively handle the adverse event and strive for the best prognosis while respecting the patient's will and choice. Meanwhile, possible adverse events are prevented and treated. As metformin was used in this study, it was expected that possible adverse events in this study would include: gastrointestinal reaction conditions, such as abdominal pain, diarrhea, and abdominal distension. In the case of serious adverse events, the Ethics Committee and relevant health authorities will be reported within 24 hours and the subject will be treated promptly.

十三、 Statistical Analysis Plan

SPSS 22.0 statistical analysis software was used for calculation. All statistical tests were performed using a two-sided test, and $P \leq 0.05$ was considered statistically significant for the difference tested. Enumeration data were described by constituent ratio, and measurement data were described by mean, standard deviation, median, and interquartile. Statistical analysis: Appropriate methods were used for analysis according to the types of indicators. T test or Wilcoxon rank sum test was used for inter-group comparison of quantitative data, and chi-square test was used for classified data.

十四、 Testing-related Ethics

1. compliance with the requirements of the declaration of helsinki and laws and regulations

2. Each subject should read the informed consent form before inclusion, and the patient should sign the informed consent form after the doctor answers all questions of the patient (see annex for the informed consent form).
3. This study is a randomized controlled trial. The test drug metformin has been used clinically and can be used together with diet and exercise to improve blood glucose control of adult patients with type 2 diabetes. Lifestyle intervention was conducted in the control group in accordance with the principle of fairness and justice. All trials will be conducted after approval by the Ethics Committee of Huadong Hospital and accept supervision by the Ethics Committee of Huadong Hospital.

十五、 Informed consent

The optional informed consent procedures in this study are described in detail below and should be in compliance with local ethics committee regulations.

1. Subject informed consent

Subjects should provide informed written consent whenever possible. Subjects were briefed by clinicians familiar with the protocol to explain consent to participate in the study.

2. Informed consent of the agent

If the subject is unable to provide informed consent, the subject's representative may provide informed consent on behalf of the subject.

3. Withdrawal of informed consent

Informed consent briefings provided to subjects and/or their agents clearly indicated that subjects could withdraw from the study at any time without explanation and that subjects would not be prejudiced or impaired thereby. This condition should be documented in the subject file.

4. Confidentiality and privacy

Care should be taken to respect the privacy of subjects during the conduct of the study. To ensure subject privacy, submissions will be de-labeled. However, in monitoring the quality of the data and adherence to the study protocol, the auditor has access to the medical records at the hospitals participating in the study.

十六、 Research progress planning

- ① 2024.10 – 2025.3: study protocol was optimized and various preparations such as the investigator's manual and patient's diary were completed; Subjects were screened into the group; Subjects were instructed to take medications and were followed up
- ② 2025.4 – 2025.9: subjects were screened into the group; Subjects were instructed to take medications and were followed up
- ③ 2025.10 – 2026.3: subjects were screened into the group; Subjects were instructed to take medications and were followed up
- ④ 2026.4 – 2026.9: All data were entered, statistically analyzed, articles were written, and the final questions were completed.

十七、 Safety Visit

A safety visit was conducted one week after the study and any adverse events were reported.

十八、 Handling of subject information and biological samples

To ensure evaluation and supervision by the Research Coordination Center of Endocrinology Department, Huadong Hospital, Fudan University, the researchers should agree to keep all research materials (including original records, informed consent network authorization of all patients, and all CRF), and assign a special counter to lock and store them. Shelf life 15 years. All materials for this clinical study were owned by the project collaboration group organized by Huadong Hospital, Fudan University.

The samples of the subjects were tested in the test center, and the biological samples were stored in the -80°C refrigerator for a period of 5 years. After the expiration of the storage period, the biological samples were destroyed in accordance

with the Shanghai Measures for the Administration of Medical Waste and other laws and regulations, and were recorded and retained.

十九、 Data and copyright

1. Data management

1) fill in and transfer of case report form

The case report form was completed by the investigator and must be completed for each enrolled case. The completed case report forms were entered and managed by the data administrator.

2) data entry and modification

For questions existing in the case report form, the data administrator will generate a question answer form and send the questions to the investigator, who should answer and return the questions as soon as possible. The data administrator will modify, confirm and enter the data according to the investigator's answers, and then send the questions again if necessary.

3) data lock

After reviewing and confirming the correctness of the established database, the project principal, main researcher and statistical analyst locked the data. The locked data file is not changed. Problems found after data lock-in were corrected in the statistical analysis procedure after validation.

4) data processing

After all the study data were entered and locked, the database was submitted to the statistical analyst for statistical analysis according to the requirements of the statistical plan. After the statistical analysis was completed, the general and sub-reports for statistical analysis were written by the statistical analysts and submitted to the principal investigator of the trial for writing the study report.

5) Data confidentiality

All subject information used in this study must be kept strictly confidential, and information about subjects who participated in the study and who were enrolled in the study must be kept confidential. Subject information and study data will be identified by study number. Information that identifies him or her will not be disclosed to members outside the study group unless subject approval is obtained. Subject identity was to be kept confidential by all study members. The subject's profile will be

maintained in a locked cabinet for access by the investigator only. To ensure that the study was conducted as required, members of the ethics committee were provided with access to subject profiles at the study unit as necessary. No personal information will be disclosed for the subject when the results of this study are published.

All study members should keep the study data confidential. They should not inform the members other than the research group of the study data without the permission of the main investigator, and should not transfer the study data to external units without the permission of the hospital.

6) Quality control

The lead investigator organized training to ensure that the study was conducted in a standardized manner, that the case report forms were completed, and that other reports complied with GCP principles and the study protocol. All data and information must be verifiable, and all observations and findings should be verifiable in order to assure the reliability of the study data. Quality control will be applied at each stage of the study to assure reliability of all data and accuracy of study procedures. The lead investigator should ensure that the investigator followed the protocol, confirmed the accuracy of the data, and documented the completeness of the report, and obtained informed consent from all subjects prior to study initiation. Any deviations or deviations from the protocol should be reported to the ethics committee in a timely manner. When necessary, the research group will designate standard operating procedures and carry out quality control procedures at each link of the implementation of research and data processing to ensure the specification and reliability of research implementation and data operation.

2. Copyright

Authors of published articles must conform to the following guidelines for authors issued by the editorial board of international medical journals:

- 1) The author must make a substantial contribution to the conception and design of the test, the acquisition of data, or the analysis of data, and the interpretation of the results;
- 2) The author must draft and publish the article in person or contribute to important revisions to the original (data analysis, interpretation, or other important intellectual content) that have been approved by other authors during the review process;
- 3) The author must provide an approval of the final draft of the article before it is submitted to the publication for publication.

All contributors who do not meet the above criteria for authorship will be listed in the acknowledgement column of the publication, if permitted by the journal, in accordance with the guidelines for acknowledgements issued by the editorial board of the International Journal of Medicine.

二十、 References

- [2] Ren Rujing, Yin Peng, Wang Zihui, etc. *China Alzheimer's Disease Report 2021. Theory and practice of diagnostics*, 2021, 20(4):317-337.

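### The protocol does not mask the week-26 MoCA rater or the fMRI blood-flow extraction in a trial where subjects and treating staff know the arm

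*Protocol*

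**What the plan says.** Under Research method, overall design (section 七), the protocol randomises to two groups: "The subjects were randomly divided into two groups using random number method". In one, "subjects received metformin sustained-release tablets (1500mg once a day or reduced to the maximum tolerated dose if intolerable) and lifestyle intervention guidance". In the other, "Subjects in the second group received only lifestyle intervention guidance". No placebo or sham is described. The Research process section (十一) adds that "diary cards were issued to record dosing and adverse events", and schedules telephone calls about adverse events every 4 weeks.

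Study Endpoints (section 十) sets the primary outcome: "The main evaluation indexes were the changes of cerebral blood flow shown by fMRI after nasal insulin inhalation". It then sets the secondary: "The secondary evaluation index was MoCA scale score". Both are measured at V0 and again at V7 (week 26), the visit at which medication history is also taken.

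On who handles the data, section 十九 has the investigator complete the case report form, a data administrator enter it, and a statistical analyst analyse it after lock: "the database was submitted to the statistical analyst for statistical analysis according to the requirements of the statistical plan". Study data are identified by study number, under the confidentiality heading.

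The protocol does not mention blinding or masking of any role. It names no MoCA assessor and no fMRI processor, and it does not describe itself as open-label.

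**The concern.** Two features combine. The design reveals the arm to subjects and treating staff through the tablets, the tolerability-based dose reduction and the dosing diary. And both efficacy outcomes pass through a human step at which knowledge of the arm can act.

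For MoCA, that step is administration and scoring; the Appendix form includes drawings that need judgement, such as a clock worth 3 points. For fMRI, it is the choice of regions, the quality check, the exclusion of scans and the extraction of values. The protocol names no brain region for the primary endpoint, so these choices can be made with the arm known.

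At stake is detection bias in the between-group difference. Randomisation balances subjects at entry but does not act on how outcomes are later scored. A MoCA scored at week 26 by someone who knew the arm cannot be made masked afterwards by an analysis plan.

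**Working it through.** **What protection each step has**

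| Step | What the protocol provides | Is the arm concealed? |
|---|---|---|
| Subject | Open tablets or guidance alone; dosing diary | No |
| Treating staff | Dose adjustment, adverse-event calls | No |
| V7 MoCA rating | Assessor not named | Not stated |
| fMRI regions, quality check, extraction | Processor not named, no reading rule | Not stated |
| Data handling | Study numbers | Identity is protected, allocation is not |

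The V0 assessments are listed before randomisation in section 十一, so for MoCA the exposure arises at V7. Scans from both visits can be processed after allocation is known.

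**Illustration for MoCA**

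The protocol gives no figure for assessment bias, so there is none to reproduce. The inputs are:

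- 23 evaluable per arm, from Sample size assessment (section 九), which plans 27 per arm before dropout.
- Two-sided test with P<=0.05, from section 十三, taken here as a two-sample t test.
- SD of MoCA 2 to 3 points: assumed; the protocol gives none.
- Mean between-arm difference caused only by the rater, b = 0.5 or 1 point: assumed; the protocol gives none.
- True treatment effect 0.

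Degrees of freedom are 2 × 23 − 2 = 44, so the critical value is 2.015. With bias b, the t statistic is noncentral with ncp = (b/SD) × √(23/2) = (b/SD) × 3.391. The chance of P<=0.05 is Pr(|T| > 2.015).

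| b (points) | SD | b/SD | ncp | Chance of P<=0.05 |
|---|---|---|---|---|
| 0 | any | 0 | 0 | 5.0% |
| 0.5 | 3 | 0.167 | 0.565 | 8.6% |
| 0.5 | 2 | 0.250 | 0.848 | 13.2% |
| 1 | 3 | 0.333 | 1.130 | 19.8% |
| 1 | 2 | 0.500 | 1.696 | 38.2% |

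If all 27 per arm are evaluable (52 degrees of freedom, multiplier √(27/2) = 3.674), the same four rows become 9.2%, 14.7%, 22.5% and 43.8%. A larger sample makes this error more likely, not less.

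**Primary endpoint**

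No comparable figure can be given. The protocol states an SD of 20% for the blood-flow change, but nothing in it indicates how far unmasked region choice or scan exclusion might shift the difference.

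**The case against.** *Omitting a placebo is a legitimate choice.* This stands. An add-on comparison with lifestyle guidance is a design decision, and the point does not ask to change it.

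*The protocol already ranks the endpoints with this in mind.* The Research background (section 六) says that "scale collection is affected by many factors" as its reason for preferring fMRI, which it calls an objective basis for assessment, and fMRI is duly primary. This stands in part. The line is an argument for fMRI, not an admission that ratings will be biased, and the fMRI risk is probably the smaller. But the objectivity of a scan does not extend to region choice and exclusions made with the arm known.

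*Some of this may lie in a document not shown.* Coding of arms for the statistical analyst may be in the statistical plan, so it is not raised here. Processing detail may also be set elsewhere, and section 十九 allows for standard operating procedures where necessary. Who rates the outcome, and whether that person knows the arm, is trial conduct and has to be settled before the V7 visits.

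*The drift figures are assumed, and 1 point is large.* This stands. Many MoCA items on the form are right or wrong, or simple counts (digits, serial subtraction, recall, orientation, animal naming), and the drawings sit in a 5-point section. One point should be read as an extreme case.

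*Scans can be reprocessed under code later.* This is plausible, since research materials are kept for 15 years, and it makes the fMRI problem more recoverable than the MoCA one. It does not help a MoCA already scored by someone aware of the arm.

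A reader might also infer that one team makes the calls, gives the MoCA and processes the scans. The documents do not say so; they are silent on who does each. What they show is that nothing separates these tasks.

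**Conclusion.** The point holds in limited form. As written, the protocol leaves the V7 MoCA rating and the fMRI blood-flow extraction unmasked while subjects and treating staff know the arm. That can bias the secondary comparison and, probably less, the primary. It does not show that bias will occur.

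For MoCA, with 23 per arm and no true effect, an assumed drift of 0.5 point raises the chance of P<=0.05 from 5% to about 9% to 13%, and an extreme drift of 1 point raises it to about 20% to 38%. These figures rest on an assumed SD of 2 to 3 points and on assumed drifts, and they do not carry over to fMRI.

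Two stronger readings are tempting. One is that masked assessment would eliminate the bias. It would not: subjects know their arm, and expectation can affect how they perform on the MoCA. The other is that existing staff can certainly provide it. The protocol names separate investigator, data administrator and analyst roles, which makes it plausible, but it gives no staffing detail.

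The change is worth making because it is cheap and because, for MoCA, it cannot be made after week 26.

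**What to change.** Add two provisions to the protocol.

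1. **fMRI.** Export the series under a code, with the arm and any visit data that would reveal treatment removed. Fix the regions, processing steps and scan-exclusion rules before processing starts. Lock the extracted blood-flow values before the allocation list is merged.

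2. **MoCA.** Where existing staffing allows, have the V7 MoCA done by a trained team member who does not dispense tablets, make that subject's telephone calls or review the diary card, and who is not told the arm. The rater asks subjects at the start not to reveal it.

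Neither provision changes the treatment, the visits or the sample size, and no placebo is needed. The cost is protocol wording and some rota planning. The downside is small: tasks must be split within the team, and some subjects may still reveal their arm.
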